#### **Project Description:**

This is a randomized, prospective trial with the primary aim of evaluating the effectiveness of intraoperative topical steroids in decreasing the severity of swallowing difficulty following anterior cervical fusion surgery.

Principal Investigator:

[name]

## Hypothesis:

The null hypothesis is that there will be no difference in swallowing difficulty between patients who do and patients who do not receive intraoperative topical steroids in the wound at the end of the surgical case.

#### Outcomes:

To determine if topical steroids placed intraoperatively in the wound of an anterior cervical discectomy and fusion surgery reduce the incidence of postoperative swallowing difficulty using the SWAL-QOL outcome measure. SWAL-QOL will be administered pre-operatively, on post-operative day one, post-operative day two, post-operative 4-6 weeks, post-operative 3 months, post-operative 6 months, and post-operative 12 months. Differences in SWAL-QOL scores will be stratified based on levels fused (2-, 3-, and 4-levels).

The Bazaz Dysphagia Score and the Eating assessment Tool 10 (EAT-10) will be administered at the same time points to provide additional data about swallowing difficulty

Additionally, questionnaires that assess how neck and arm related pain affects the patient's quality of life will be administered pre-operatively (NDI & VAS), post-operatively day 1 and 2 (VAS), week 4-6 (NDI & VAS), month 3 (NDI & VAS), month 6 (NDI & VAS), and at month 12 (NDI & VAS).

### Background:

Swallowing difficulties are a major side effect of anterior neck fusion surgery. Steroids have the effect of reducing inflammation and swelling, factors considered likely to cause swallowing difficulties following anterior neck surgery. This study looks to determine if steroids placed into the wound at the end of an anterior neck fusion surgery decrease the severity of a patient having swallowing difficulty following the surgery.

Dysphagia is a serious post-operative concern in patients following anterior cervical surgery. Although many authors have acknowledged that dysphagia is often incompletely understood and defined, there is a significant amount of literature to support the significance of this clinical entity. Lee et al (The Spine Journal 2007) found the incidence of post-operative dysphagia at 1, 2, 6, and 12 months post-operatively to be 54.2%, 33.6%, 18.6%, 15.2%, and 13.6%, respectively. Rihn et al (CORR 2011) found the

incidence to be 71% at two weeks post-operatively. Bazaz et al (Spine 2002), found it to be 50.2%, 32.2%, 17.8%, and 12.5% at 1, 2 6, and 12 months post-operatively. Moreover, Lee et al (Spine 2010) performed a systematic review and found in 17 studies the average incidence of dysphagia to be 13-21% at one-year post-operatively.

This study will utilize a validated questionnaire, SWAL-QOL, to evaluate swallowing difficulty and dysphagia. In addition, the study will investigate these outcomes in 2-4 level ACDFs, which have not been examined previously.

If topical steroid use can be proven to be safe and effective, it is a relatively inexpensive, easy measure to institute to diminish the occurrence of a serious complication following anterior cervical surgery and improve patient-reported outcomes.

This is a randomized, prospective clinical trial.

Study Drug:

Depo-Medrol (Methylprednisolone acetate)

This drug is FDA-approved and being utilized in an "off-label" manner. We confirmed with clinical research administration that the use of this drug does not require notification to the FDA or filing of an IND.

Inclusion Criteria:

Any patient > 18 years undergoing a 2-4 level anterior cervical discectomy and fusion

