#### Interventions and Observations:

We plan to observe the effect on SWAL-QOL scores in patients following ACDF in groups that either receive or do not receive intraoperative topical steroid. All individuals undergoing 2-4 level ACDF that meet the inclusion criteria will be randomized to either: 1) treatment arm or 2) control arm. Both arms will undergo their planned surgeries and will receive the exact same procedure and standard of care as if they were not enrolled in a study. The only difference is that the treatment arm will receive 40 mg of Depo-Medrol delivered with one SURGIFLO Hemostatic Matrix Kit (Ethicon, Somerville, NJ, USA) injectable delivery vehicle prior to closure in the prevertebral soft tissues. The control group will receive only SURGIFLO Hemostatic Matrix Kit prior to closure. The surgeon will inject the material directly in the pre-vertebral soft tissue.

Both groups will have the same standard evaluations both pre-operatively and post operatively. The SWAL-QOL questionnaire will be utilized as the primary instrument to measure outcome. Other questionnaires, the EAT-10 and Bazaz Dysphagia Score, which grades will be used to assess dysphagia and swallowing difficulty. Additionally, the Neck Disability Index and the Visual Analog Scale for neck and arm pain will be administered to assess how neck related pain impacts the patients' quality of life. The EAT-10, Bazaz, and Visual Analog scale will be utilized to assess secondary outcomes. These questionnaire will be given to the patients to complete pre-operatively, on post-operative day one, post-operative day two, at post-operative week 4-6, post-operative month 3, post-operative month 6, and post-operative month 12. The Neck Disability Index will be completed pre-operatively, at post-operative week 4-6, post-operative month 12.

All test or images are standard of care. Administration of the EAT-10, SWAL-QOL survey, Neck Disability Index, VAS (Neck and Arm Pain), and Bazaz Dysphagia Score are not standard of care. Funds are not required for administration of these questionnaires.

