# **Statistical Plan:**

Steroid and Control arms were compared in terms of demographics and surgical information using a student's independent t-test and chi square/fisher exact test for normally distributed data, and a Mann-Whitney U test otherwise. In terms of PROs, a Mann-Whitney U test was performed to compare the group medians for dysphagia scores at Baseline, Post-op Day 1, Post-op Day 2, post-operative week 4-6, post-operative month 3, post-operative month 6, and post-operative month 12. In addition, a pre-post op comparison was conducted by calculating the change in PRO from baseline to each post-operative time point for each patient. Statistical significance was determined for all results with p<0.05.

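### No adverse event or surgical complication is pre-specified or compared by arm, although the Background makes adoption of the steroid conditional on safety

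*Combined protocol and SAP*

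**What the plan says.** **Rationale.** The Background presents the steroid as a cheap and simple measure, on a condition: "If topical steroid use can be proven to be safe and effective". The same section says that the drug is used off-label.

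**Aim and hypothesis.** The Project Description gives the primary aim as "evaluating the effectiveness of intraoperative topical steroids in decreasing the severity of swallowing difficulty". The Hypothesis section reads "The null hypothesis is that there will be no difference in swallowing difficulty" between patients who do and do not receive the steroid. Neither mentions harm.

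**Outcomes.** The Outcomes section lists SWAL-QOL, the Bazaz score, EAT-10, the Neck Disability Index and VAS pain, with time points up to month 12. Interventions and Observations adds "The SWAL-QOL questionnaire will be utilized as the primary instrument to measure outcome" and "The EAT-10, Bazaz, and Visual Analog scale will be utilized to assess secondary outcomes".

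**Other data.** Interventions and Observations also states "Both groups will have the same standard evaluations both pre-operatively and post operatively" and "All test or images are standard of care". It does not say what those evaluations, tests or images are, when they take place, or whether any of them is study data.

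**Analysis.** The Statistical Plan says "Steroid and Control arms were compared in terms of demographics and surgical information". It then compares dysphagia scores at each visit and calculates changes from baseline in the patient-reported outcomes. It has no analysis of events or complications.

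**The concern.** The Background names two conditions for taking up the treatment, and the design collects evidence on one of them. The drug is injected into the pre-vertebral soft tissue before closure of a 2-4 level fusion, a range of levels that the Background describes as not previously studied. Patients with an active infection or a known allergy to the drug are excluded at entry, but no infection or allergic reaction is recorded as an outcome afterwards. The Randomization section allows for early stopping but names no safety data that could inform it.

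What is at stake is the use made of a positive swallowing result. It could support adoption of the steroid although the one randomised comparison available had not looked for an imbalance in complications. A reader could also take the absence of reported harm as evidence of safety, when events had simply not been counted.

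**Working it through.** **Step 1: look for a safety outcome, section by section.**

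| Section | Content | Adverse event or complication named? |
|---|---|---|
| Project Description | effectiveness for swallowing severity | no |
| Hypothesis | swallowing difficulty | no |
| Outcomes | SWAL-QOL, Bazaz, EAT-10, NDI, VAS | no |
| Interventions and Observations | the same questionnaires; unspecified standard evaluations and images | no |
| Randomization | possible early stopping | no criterion or data item |
| Statistical Plan | demographics, surgical information, patient-reported scores | no |

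The only item that might hold complications is the surgical information in the Statistical Plan. The term is undefined and stands beside demographics as a description of the arms. It cannot be read as a pre-specified safety outcome running to month 12.

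**Step 2: what could safety data show at this size?** The plan gives no safety figure to reproduce. The only sample-size figure is the Target Enrollment of 128, which has no stated derivation.

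Inputs:
- Total 128, from Target Enrollment.
- 64 per arm = 128/2. This is an assumption: Randomization speaks of equivalent numbers in each group but states no ratio, and no dropout is given.

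Exact upper limit for the true rate after 0 events in n patients: 1 − α^(1/n), with α = 0.05 (one-sided 95%) or 0.025 (upper end of a two-sided 95% interval).

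- n = 64, one-sided: 1 − 0.05^(1/64) = 0.0457, or 4.6%.
- n = 64, two-sided: 1 − 0.025^(1/64) = 0.0560, or 5.6%.

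Dropout raises both limits. For illustration, with assumed losses of 10% and 20%:

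| Assumed loss | n per arm | One-sided 95% | Two-sided 95% |
|---|---|---|---|
| none | 64 | 4.6% | 5.6% |
| 10% | 58 (64 × 0.9 = 57.6) | 5.0% | 6.2% |
| 20% | 51 (64 × 0.8 = 51.2) | 5.7% | 7.0% |

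Chance of seeing no event in 64 treated patients, (1 − p)^64:
- p = 1%: 0.99^64 = 0.526, or 53%.
- p = 2%: 0.98^64 = 0.274, or 27%.

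**Step 3: could a test between arms settle it?** Power of a two-sided Fisher exact test at 0.05 with 64 per arm, for assumed control and steroid rates (none is in the documents):
- 1% against 5%: 6%.
- 2% against 10%: 31%.
- 5% against 15%: 36%.
- 5% against 20%: 67%.

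A hypothesis test on complications would therefore say little. Counts with intervals are the appropriate form of report.

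**The case against.** The strongest reply is that safety is not an objective of this trial. The sentence on safety and effectiveness is a conditional in the Background. It does not promise that this study will prove safety, and the aim and hypothesis cover effectiveness alone. That stands. A reader might infer that the plan sets out to prove safety and leaves half of its own question unanswered; the documents do not support this. The gap lies between the rationale and the outcomes, and no stated objective goes unmet.

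A reader might also infer that the trial would yield no information on harm at all. That is too strong. The swallowing, pain and disability scores could show worsening as well as benefit, both arms receive standard evaluations, and the content of the surgical information is unknown. None of these is designated or analysed as a safety outcome, however, and the questionnaires would not identify an infection or a re-operation as such.

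Two further objections stand in part:
- The limits in the working measure how imprecise safety data would be. They do not measure the loss from failing to collect them. They are a reason to report descriptively and to soften the wording, and no reason to leave events uncounted.
- The documents give no imaging schedule, so fusion status cannot be promised for every patient at no added cost. It can be reported only where images already exist.

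Finally, no section links the drug to a particular complication. The list of events in the fix is a reasonable general choice after surgery of this kind; the plan does not identify these as risks of the drug.

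**Conclusion.** The point holds in a limited form. No adverse event or complication is defined, collected as an outcome or compared by arm, so the trial as written cannot inform the safety condition in its own rationale. The efficacy analysis is unaffected.

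The numbers bear on what may be claimed once events are counted. On the assumption of 64 per arm with complete follow-up, an arm free of events would still be compatible with a true rate of up to 4.6% or 5.6%, depending on the limit used, and a complication with a true rate of 1% would be missed altogether in about half of such trials. The word proven is therefore out of reach for safety at this size, with or without the added outcome. The change is worth making because it is cheap and because it alters what the trial can say about harm.

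**What to change.** 1. **Outcomes.** Add a descriptive secondary safety outcome covering surgical-site infection, allergic reaction, readmission and re-operation through month 12. Give each a short definition. Take the events from existing records, with abstraction by someone unaware of allocation where feasible.
2. **Statistical Plan.** Report each event by arm as a count and a rate with an exact 95% confidence interval, and give a 95% confidence interval for the difference between arms. State that the comparison is descriptive and that the absence of a difference will not be read as evidence of safety.
3. **Fusion status.** Report it only for patients with standard-of-care images, and state how many patients in each arm have them.
4. **Background.** Reword the sentence so that the trial evaluates effectiveness and describes safety.

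**Cost.** Modest chart-review time, short event definitions and one additional table. The intervals will be wide and must be shown. The four record-based events call for no new test, and fusion is limited to images that already exist.

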### **Exclusion Criteria:**

- Revision surgery
- Pediatric patients
- Patients with Cervical vertebra fracture(s)
- Patients with Cervical Spine Tumors
- Patients with active infection
- Patients with a known allergy to Depo-Medrol
- Patients who refuse to participate
- Non English speakers

Age Range:

>18 years

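### Eligibility does not exclude a known swallowing disorder from another cause, which costs power and interpretability because the only named between-arm test ignores the pre-operative score

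*Combined protocol and SAP*

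**What the plan says.** Under Inclusion Criteria (within Background), the combined protocol and SAP admits "Any patient > 18 years undergoing a 2-4 level anterior cervical discectomy and fusion". The Exclusion Criteria list eight items: "Revision surgery", paediatric age, cervical fracture, "Patients with Cervical Spine Tumors", active infection, "Patients with a known allergy to Depo-Medrol", refusal, and not speaking English. None refers to pre-existing dysphagia, or to neurological, oesophageal or head-and-neck disease.

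On mechanism, Background states: "Steroids have the effect of reducing inflammation and swelling, factors considered likely to cause swallowing difficulties following anterior neck surgery". The Outcomes section gives the aim as to "reduce the incidence of postoperative swallowing difficulty using the SWAL-QOL outcome measure". It sets no score cut-off and no rule for a patient already impaired before surgery.

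A baseline is measured: "SWAL-QOL will be administered pre-operatively, on post-operative day one" and at the later visits, with EAT-10 and the other dysphagia scale at the same times. In the Statistical Plan, "a Mann-Whitney U test was performed to compare the group medians for dysphagia scores at Baseline" and at each post-operative visit. As an additional step, each patient's change from baseline is calculated. No between-arm test is named for that change, and it is not designated primary. Randomization is stratified by procedure, not by baseline swallowing.

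**The concern.** The trial asks whether a topical steroid reduces swallowing difficulty that follows surgery. A patient whose dysphagia was known beforehand and has another origin fits that question poorly in three ways:

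- The score is likely to be poor at every visit, which widens the spread within each arm.
- To the extent that the deficit is not surgical swelling, the stated mechanism gives no reason to expect it to improve, so the average difference between arms may shrink.
- The patient is already a case before surgery and so cannot be a new one, although the Outcomes section speaks of incidence.

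The unadjusted comparison at each visit does not separate this older deficit from a surgical one. What is at stake is the power of a 128-patient trial and the clarity of its answer.

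**Working it through.** **The plan's own figure.** Target Enrollment is 128, with no effect size, SD, power or dropout stated, so it cannot be reproduced from the documents. As an assumption only: a two-sided 5% t-test with 80% power and a standardised difference of 0.5 needs 63.8, so 64, per arm, or 128 in all. That match does not identify the basis, but it gives a starting point.

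**Inputs.**
- From the documents: 128 patients; p<0.05 (two-sided assumed); equal arms intended (64 per arm assumed).
- Assumed: SD 15 and a true effect of 7.5 points (d = 0.5) in patients without a prior disorder; a share q of affected patients; affected patients scoring 15 or 25 points lower (15/15 = 1.0 SD, 25/15 = 1.7 SD).

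**Formulas** for the unadjusted comparison (t-test power):
- Variance = 225 + q(1 − q) × gap².
- No benefit in affected patients: d = (1 − q) × 7.5 / SD.
- Equal benefit in affected patients: d = 7.5 / SD.

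Example, q = 10%, gap 25: variance = 225 + 0.10 × 0.90 × 625 = 281.25, so SD = 16.77. With no benefit, d = 6.75/16.77 = 0.402 and power is 62%. With equal benefit, d = 7.5/16.77 = 0.447 and power is 71%.

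| q | SD (gap 15 / 25) | d, no benefit | Power, no benefit | d, equal benefit | Power, equal benefit |
|---|---|---|---|---|---|
| 0% | 15.00 | 0.500 | 80% | 0.500 | 80% |
| 1% | 15.07 / 15.20 | 0.493 / 0.488 | 79% / 78% | 0.498 / 0.493 | 80% / 79% |
| 2% | 15.15 / 15.40 | 0.485 / 0.477 | 78% / 76% | 0.495 / 0.487 | 79% / 78% |
| 5% | 15.35 / 15.96 | 0.464 / 0.446 | 74% / 71% | 0.489 / 0.470 | 78% / 75% |
| 10% | 15.66 / 16.77 | 0.431 / 0.402 | 68% / 62% | 0.479 / 0.447 | 77% / 71% |
| 15% | 15.93 / 17.46 | 0.400 / 0.365 | 61% / 54% | 0.471 / 0.430 | 75% / 67% |

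The loss has two parts. At 10%, dilution alone (d = 0.45, SD unchanged) gives 71%; spread alone is the equal-benefit column, 71-77%. Adjustment for baseline can recover much of the second part but not the first.

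**Check with the planned test.** A Mann-Whitney simulation used 2,000 runs, 64 per arm, a shift of 0.52 SD, affected patients 2 SD worse, and a baseline correlation of 0.5.
- Raw scores: power is about 81% with no affected patients. At 10% affected it is 64% with no benefit in them and 70% with equal benefit.
- Change scores: 82% with no affected patients. At 10% affected, 72% with no benefit and about 81% with equal benefit.
- Change scores depend on the correlation. At 0.3 they start at only 66-68%; at 0.7 they start at about 95%.

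**The incidence aim.** Suppose cases were counted with no baseline rule. Take the one-month rate of 50.2% cited in Background as the control rate, against 26.3%, the rate that 64 per arm would distinguish with 80% power. If 10% were cases in both arms regardless, the rates become 0.10 + 0.90 × 0.502 = 55.2% and 0.10 + 0.90 × 0.263 = 33.7%, and power is 69%. This is an illustration, because the Statistical Plan contains no such count.

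**The case against.** The strongest reply is that the plan already holds most of the remedy. Scores are taken before surgery, the arms are compared at baseline, and change from baseline is calculated for each patient, so a stable earlier deficit cancels. This stands in part. With equal benefit, the simulated change-score power does not fall. But the change is an additional calculation with no between-arm test named, and it does not undo dilution where the steroid does not help.

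Second, zero benefit is a worst case. These patients have the same operation and can have the same swelling, so part of their difficulty may respond. This stands, which is why both columns are shown.

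Third, no prevalence is documented, and the exclusions for revision, tumour, fracture and infection already remove some other causes. At 1-2% even the worst case leaves 76-79%. This stands; the loss may be small.

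Fourth, broad entry can be a legitimate choice, and the Hypothesis and Background speak of swallowing difficulty and its severity without limiting these to new cases. That is fair, but the plan does not state broad entry as a choice, and its named test is not built for it.

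A reader might infer two stronger things. One is that such patients will be counted as post-operative dysphagia in either arm. The Statistical Plan has no case definition or case count, so this bears only on the incidence wording in Outcomes. The other is that the comparison is biased. Randomisation balances these patients in expectation, and the test's type I error already allows for chance imbalance. An uneven split would still make a single result harder to read: if 12 of 128 were affected, a split of 8-4 or worse arises in about 36% of 64/64 allocations (hypergeometric).

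**Conclusion.** The point holds as an avoidable loss of power and interpretability, and the sponsor should address it. It is neither a systematic bias nor a fault that invalidates the design. Eligibility lets in patients with a known swallowing disorder from another cause, and the only named between-arm test takes no account of their pre-operative score.

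From 80%, unadjusted power would be 76-79% at 1-2% prevalence, 71-74% at 5% and 62-68% at 10% if these patients gain nothing, and 75-78% at 5% and 71-77% at 10% if they gain as much as the others. So the loss is trivial at 1-2% and material at 10%.

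These figures rest on an assumed effect of 0.5 SD, an assumed score deficit of 1.0-1.7 SD, full follow-up of 64 per arm, and a t-test standing in for the rank test. None of the prevalence, effect size or SD values comes from the documents. That the gap exists is certain; its size is not.

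**What to change.** Add one line to the Exclusion Criteria: *Documented swallowing disorder from a cause other than the cervical spine condition, known before surgery.* This keeps patients whose dysphagia comes from the spine condition itself. The cost is slightly slower recruitment and a narrower population.

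If broad entry is preferred, say so and do four things:

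1. Record any such diagnosis before randomisation, since a baseline score does not show its cause.
2. Define post-operative dysphagia as new or worsened from the pre-operative score.
3. Compare the arms with adjustment for pre-operative SWAL-QOL (ANCOVA or its rank version). Unlike a plain change score, this does not lose precision when the baseline correlation is low.
4. Report a sensitivity analysis without these patients.

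The second route needs one extra baseline item and otherwise uses data already planned. Neither route changes the intervention or the visit schedule.
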